2.2.3 Procedures for MRI Examination (Visits 2, 3)

The following procedures will be performed:

1. Run the patient on a 10-minute fMRI exam during visits two and three:
 - Instruct the patient to overtly name pictures representing nouns (n = 40) once they appear on the screen and to say nothing when abstract pictures (n= 20) appear on the screen
 - The pictures will be presented for 2 s each on a back-projected mirror located on top of the head coil
 - A non-ferrous microphone will be placed 1-3 cm from the patient's mouth and used to record naming attempts, which will be recorded with sufficient clarity for off-line scoring by a trained speech-language pathologist
2. Run the patient on high-resolution anatomical MRI scans during Visit 2:
 - Instruct the patient to do nothing during these scans

2.2.4 Procedures for the Computerized Naming Assessments (Visits 2, 3, 19-24)

The following procedures will be performed during Visits 2, 3, and 19-24:

1. Turn on the laptop computer and position in front of the patient
2. Set up and start internal web-camera for audio-visual recording.
3. Administer the combined *Philadelphia Naming Test* (PNT; Roach et al., 1996) on a laptop computer. *Note to clinician: The PNT (175 items) will also include 80 treated pictures for a total of 255 picture presentations:*
 - Instruct the patient to overtly name each picture as soon as it is displayed
 - Trials will end following a response or after 20-seconds have elapsed, in which the administrator will say the correct picture name in order to discourage perseveration on subsequent trials
4. Stop web-camera and save video file for later scoring of naming.

2.2.5 Procedures for the “Cinderella Story” picture discourse analysis (Visits 3, 19, 21, and 23)

The following procedures will be performed during Visits 3, 19, 21, and 23:

[figure not shown]
1. To be completed following the administration of the CNA-PNT, so the laptop computer and web-camera set-up will need to remain for this portion of the assessment
2. Place the picture book in front of the patient
3. Tell the patient, "I'm going to ask you to tell a story. Have you ever heard the story of Cinderella?" (Make note of answer) "Do you remember much about it? These pictures might remind you of how it goes. Take a look at the pictures and then I'll put the book away, and ask you to tell me the story in your own words." Allow the patient to look through the book (assist with page turning, if needed) and then, if necessary, prompt: "Now tell me as much of the story of Cinderella as you can. You can use any details you know about the story, as well as the pictures you just looked at." Continue until the patient concludes the story or it is clear s/he has finished.
4. Stop web-camera and save video file for later transcription

[figure not shown]
2.2.6 Procedures for Electrode Positioning (Visit 4)

The following procedures will be performed:

1. Fit the patient with a latex scalp cap and instruct them to sit as still as possible during this process
2. Identify and label the following six anatomical landmarks on the patient's scalp cap utilizing a permanent marker: 1) left ear; 2) right ear; 3) left eyebrow; 4) right eyebrow; 5) head apex; and 6) occipital bun
3. Upload the patient's anatomical T1 MRI scan (acquired from Visit 2) onto a computer utilizing *MRicro*, a computer program that allows for the viewing of MRI images.
4. Employing *MRicro*, select an anatomical location on the patient's T1 MRI scan (e.g., bridge of nose) by mouse-click
5. Move the magnet sensor from the *Flock of Birds* magnetic tracking system to the location on the patient's head which mirrors the anatomical position selected in *MRicro* from Step 4 and enter into the *MRireg* software, a computer program that registers a high-resolution MRI scan of the head with scalp locations
6. Repeat Steps 4 and 5 until the following five anatomical landmarks have been entered into *MRireg*: 1) left ear; 2) right ear; 3) bridge of nose; 4) head apex; and 5) occipital bun
7. Press the 'correlation line' button of *MRireg* after the five anatomical landmarks from Step 6 have been located
8. Enter the coordinates of the area of the left hemisphere with the highest level of activation within the peri-lesional area during correct naming on the fMRI naming task in the 'desired MRI' boxes (these coordinates will be identified by Dr. [name] and forwarded to you [SLP] on patient-by-patient basis)
9. *MRireg* will estimate the current distance of the magnet sensor wand from this point. Move the wand around the patient's head and once the most precise area is located, label the location on the patient's scalp cap with a star utilizing a permanent marker

Below: Example of Step 4

Left: Example of Steps 8 & 9. The 'desired MRI boxes' are displayed. Additionally, the current distance of the magnetic sensor from the coordinates entered in the 'desired MRI boxes' is displayed, which in this example, is 30.9 mm.

2.2.7 Procedures for Collection of Blood sample (Visit 4)

1. Collection of blood samples will be handled by the study coordinators (both are registered nurses) assisting Drs. [name] and [name]
2. Once blood sample has been obtained, write patient number (as generated by the DCU) on the vial
3. Follow storage procedures as advised by [name] lab at MUSC
4. At USC, place the blood sample in the lab freezer in [name] lab
5. At MUSC, place the blood sample in the designated lab freezer in [name] lab

[figure not shown]
2.2.8 Procedures for Treatment (Visits 4-18)

The following procedures will be performed:

1. Measure and record the patient's blood pressure and heart rate
2. Carefully fit patients with their scalp cap (labeled from Visit 4)
3. Soak the 2 sponge electrodes in saline solution and place inside rubber electrode holders
4. Place the anode electrode under the designated area on the scalp cap that was located during the electrode positioning process (marked with a star during Visit 4). Remove the cap and secure electrode placement with a self-adhesive bandage
5. Place the reference cathode electrode on the patient's right orbito-frontal scalp (above the right eyebrow) and secure electrode placement with a self-adhesive bandage
6. Connect the electrode cables to the relay box positioned between the tDCS stimulator and the lap-top computer used to maintain experimenter and patient blinding. Start the software used for blinding (see an icon "tDCS+aphasia" on the desktop) and enter the patient number (obtained on the DCU web site) in the designated place. Make sure that the screen of the "blinding" lap-top is placed out of patients' sight.
7. Turn on tDCS stimulator
8. Set-up the computerized anomia task:
 - o Turn on computer and position in front of patient
 - o Plug in the red/green response buttons into the computer and position in front of patient
 - o Plug in the earbud headphones into the computer and place in patient's ears

- Play example sound clip to verify with patient that sound is sufficient; if sound is not sufficient, adjust volume until patient is satisfied
 - Locate the patient's designated treatment folder and open
9. Instruct the patient how to perform the self-administered computerized anomia treatment consisting of a picture-word matching task, which will be coupled with the stimulation
- The computerized treatment task will be 45-minutes in total length, so that it will commence at the same time as the tDCS administration
 - A picture will be presented for 2 s on a laptop computer screen and will be immediately followed by an audio-visual display of a male speaker's mouth saying a noun. Video of the speaker producing the noun is presented in synchrony with the audio via in-ear headphones. The spoken word either will or will not match the preceding picture. In the event of a match, instruct the patient to press a large green response button interfaced with the computer, and in the case of a non-match, instruct the patient to press a red button. Half of the picture/word pairs will match, while the other half will not. The computer will provide immediate visual feedback following a response in the form of a "smiley face" for correct answers and a "frowny face" for incorrect answers. Additionally, following the completion of a treatment session, a data file of the patient's responses will be automatically saved, and the accuracy score from that session will be displayed on the computer screen.

Right: Example of the computerized treatment task. The picture representation for "cat" does not match the subsequent audio-visual presentation for "leg." Since the pair is not a match, the red button was correctly pressed, which lead to the immediate "smiley face" feedback.

10. "Click" on the START icon on the "blinding" computer to simultaneously start stimulation and the computer treatment task
11. Measure and record the patient's blood pressure and heart rate following treatment completion
12. Record any Adverse Events experienced during the treatment session or since the last visit on the AE log.
13. Assess and record the patient's comfort rating using the *Wong-Baker FACES Pain Rating Scale* following treatment completion

Left: A reproduction of the "Wong-Baker FACES Pain Rating Scale"

2.2.9 Procedures for Neurological Examination (Visits 8, 13, 18)

The following procedures will be performed:

1. All patients will be monitored closely for safety and neurological functioning during the duration of the study. In addition to the comfort ratings recorded daily the neurological examination administered during Visit 1 will be re-administered weekly by Drs. [name] or [name] during the treatment phase.

2.2.10 Record medications for each patient.

A list of all current medications should be recorded in the appropriate location in WebDCU.

3. STATISTICAL CONSIDERATIONS FOR THE PRIMARY STUDY AIM

3.1 Analysis Sample

The primary analysis will be analyzed under the intent-to-treat principle (ITT). Under this principle, the evaluable sample will include all participants who are randomized regardless of the type of treatment that was actually administered. For the safety analyses, all randomized participants who receive at least one session of the treatment will be included, regardless of the duration of treatment administered.

3.2 Randomization and Blinding

The study is to be conducted in a double-blind manner. The subjects, the site investigators, and the USC and MUSC clinical staff involved in this study will not know the treatment assignment. Select members of the Statistical and Data Management Center will be partially blinded, i.e., they will know the treatment group assignment as A or B, but not whether the patient receives active tDCS or sham. The study statistician and the DSMB will have a sealed envelope with the treatment group identifiers. This envelope would only be opened if the study statistician is directed to open it by the DSMB or at the end of the futility study.

The randomization will take place centrally via the Trial Website. Subjects will be randomized 1:1 (A-tDCS: S-tDCS), controlling for clinical center, aphasia type, and severity (classified using the Western Aphasia Battery revised: WAB-R). The computer program developed at the DCU makes the treatment assignment based on the current status of treatment group distribution within each stratum as well as overall balance of treatment assignment. The randomization scheme will never be deterministic. The detailed randomization scheme and source codes will be provided in the Randomization Plan document.

A “Real-Time” randomization procedure is implemented via the Trial Website on the WebDCU™ System where the clinical center staff enters the basic baseline (e.g. aphasia type, and AQ severity) and eligibility information of a subject prior to enrollment. If the subject’s eligibility status is confirmed, the computer program on the WebDCU™ server will evaluate the treatment arm distribution and generate a patient number based on the randomization scheme. The SLP enrolling the patient will not see the treatment assignment, only a numeric patient number which is entered into a software package that controls whether the tDCS given is A-tDCS or S-tDCS. In order to mask treatment type (A-tDCS vs. S-tDCS) for both patients as well as the SLPs administering the treatment session (ie. setting up the tDCS and starting and monitoring the computerized treatment task), we use in-house software/hardware. As previously discussed, this setup allows for switching the tDCS on and off without any involvement from the patient or experimenter. The software is run on a lap-top computer connected to the tDCS stimulator. Treatment type is encoded in the software so that the administrator only needs to enter a patient and session number to start stimulation without knowing whether those specific numbers are

associated with A-tDCS or S-tDCS. The unblinded list of randomization codes and treatment assignments will be generated by the DCU and will be uploaded into the software by a software administrator who is not otherwise involved in the study.

3.3 Baseline Treatment Group Comparability

During the course of the study as a part of the DSMB reports, summary statistics for the following baseline variables will be computed and compared between treatment groups: age, gender, years of education, WAB-R, BNT-2, ABA-2, PPTT, and WAIS subtest. At study conclusion, the statistical tests for comparison will be two-sample t-test or Wilcoxon rank sum test for continuous scale variables and chi-square or exact test for categorical variables.

3.4 Primary Analysis

3.4.1 Primary Outcome

The primary outcome will be defined as the change in number of correctly named items on the PNT (pre-treatment and immediate post-testing). To assess change in naming ability, the primary outcome in this study, the PNT (plus a portion [N=80] of the trained items) will be administered twice (and averaged to reduce variability) on two consecutive days immediately before treatment starts and twice after treatment is completed. The change will be computed as the difference in the number of correctly named items comparing the average of the two pre-treatment PNT assessments to the average of the two post-treatment PNT sessions.

3.4.2 Statistical Hypotheses

The primary hypothesis is:

$$H_0: \mu_T - \mu_S \geq \delta$$

vs.

$$H_A: \mu_T - \mu_S < \delta$$

where μ_T is the expected change (pre-treatment and immediate post-testing) in the number of correctly named items for the treatment arm, μ_S is the expected change in the sham control group, and δ is the minimum improvement sufficient to warrant further evaluation of tDCS treatment. We define that minimum improvement to be 1.5 points more than the observed change in the sham control group. If we reject the null hypothesis, then tDCS is considered clearly ineffective (in improving anomia in stroke patients) and will not be considered for further study. If we fail to reject the null hypothesis, we would consider undertaking a Phase III study of tDCS.

3.4.3 Sample Size Determination

In preliminary studies, the mean difference in change from baseline in the active and sham groups in naming accuracy was ~2.5 points (Baker, Rorden, & Fridriksson, 2010, Fridriksson et al., 2011). In one study, the S-tDCS (sham) group improved ~1.2 point from baseline to 1 week (Baker, Rorden, & Fridriksson, 2010). In another study, the S-tDCS group improved ~3.9 points from baseline to 1 week (Fridriksson et al., 2011). For power calculations, we assumed the mean change from baseline to immediate (1 week) post-testing for the A-tDCS group under the

null hypothesis of non-futility is equal to $m_s+d=4+1.5=5.5$. When the sample size is 33 per group, a two sample t-test with a 0.10 one-sided significance level will have 85% power to reject the null hypothesis that the A-tDCS treatment is 1.5 points better than S-tDCS (sham) and declare futility when the A-tDCS treatment comes from a distribution with mean change of 4 (assuming the pooled SD is 2.6). As with most clinical studies, a certain amount of drop-outs (including subject withdrawal or lost-to-follow-up) can be expected. In preliminary studies less than 5% of visits were missing. Conservatively assuming the drop-out rate to be no more than 5% over 5 weeks, the required sample size was inflated from 33 to 37 per treatment arm to account for the effect of the drop-outs in the intent-to-treat analysis using an inflation factor (Friedman, et al, 1985).

3.4.4 Multiplicity

Since this is a phase II study, the false positive error rate has been relaxed (Schoenfeld 1980). For a futility design the type I and type II error rates are reversed as compared to a traditional, superiority hypothesis. For the primary analysis, the probability of incorrectly declaring a drug futile is 0.1 (or 10%, type I error is the false negative rate). Given that the active tDCS comes from a distribution with a mean change of the control group (e.g. the treatment is the same as the sham), the probability of incorrectly moving to a Phase III trial is 0.15 (or 15%, type II error is the false positive rate).

For secondary outcomes and safety analyses, no adjustment of Type I error probability will be considered, since they will be treated as exploratory.

3.4.5 Missing Data

Under the ITT principle, all patients who are randomized are included in the analysis. Therefore, missing data, especially in the primary outcome measure, can be problematic. For the primary futility analysis we will impute missing data using multiple imputation (Rubin, 1987) assuming a monotone missing mechanism and missing is at random (MAR). Similar methods will be employed for secondary analyses and secondary outcomes. For safety data (e.g. AEs) no data imputation will be done.

3.4.6 Interim Analysis

No formal interim analyses are planned.

3.4.7 Adjusting for Covariates

The primary analysis will be adjusted for clinical site, aphasia type, and baseline aphasia severity (AQ).

3.5 Secondary Analyses

3.5.1 Secondary Efficacy Outcome measures

In addition to the primary outcome, several secondary analyses will be conducted. We will examine changes in types of naming errors (defined by the PNT) by tDCS treatment group. The Cinderella story will be analyzed by comparing lexical diversity (VOCD) for nouns, verbs and adjectives; number and types of errors; length and patterns of pauses by treatment group. Pre and post comparisons with both non-aphasic and aphasic speakers from the Aphasia Bank database who share a number of demographic features (e.g., type and severity of aphasia, age, etc) will also be made.

At the end of the study, for the interval scale variables, mean change from baseline to

immediate post-testing in secondary outcome measures will be reported by treatment group along with the 95% confidence intervals. Treatment comparisons will be made with a paired t-test. For binary variables, the proportion of subjects immediately post-testing will be reported by treatment group along with the 95% confidence intervals.

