2. STUDY PROCEDURES

2.1 Study Procedures Overview

After informed consent is received, a neurological examination will be performed and multiple screening assessments will be conducted including a tDCS and MRI safety screening (see below). If the patient passes the initial screening portion, speech and language diagnostic testing will be conducted during the same visit (Visit 1). During the next two visits (Visits 2 and 3), patients will undergo baseline assessments of naming ability and connected speech, and structural and functional MRI examinations. The fourth visit will include collection of blood sample, electrode positioning and tDCS treatment administration. Patients will receive 15 sessions (Visits 4-18) of tDCS treatment administration. At the beginning of Visit 4, eligible patients will be randomized to receive either A-tDCS (1 mA) or S-tDCS (placebo) for 15 consecutive weekdays (20-min per each 45-min behavioral treatment session). A computerized anomia treatment will be coupled with the stimulation. The computerized treatment task will be 45-minutes in total length, so that it will commence at the same time as the tDCS administration and continue for another 25-minutes after the tDCS has ceased. To assess cardiovascular arousal, blood pressure and heart rate will be measured before and after each session. Additionally, discomfort ratings will be recorded following the end of each session using the *Wong-Baker FACES Pain Rating Scale* and a weekly neurological exam will be administered by a neurologist. Utilizing a computerized picture naming assessment (which combines the 175 items from the PNT and 80 treated items) of trained and untrained nouns, all patients will be assessed at 8 different time points throughout the experiment: twice at baseline (Visit 2 and 3), twice immediately following the fifteenth (and final) treatment session (Visit 19 and Visit 20), twice at 4 weeks follow-up (Visit 21 and Visit 22), and twice at 6 months follow-up (Visit 23 and Visit 24).

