6. RANDOMIZATION AND BLINDING

The study is to be conducted in a double-blind manner. The subjects, the site investigators, and the USC and MUSC clinical staff involved in this study will not know the intervention assignment. Select members of the Data Coordination Unit (DCU) will be partially blinded, i.e., they will know the intervention group assignment as A or B, but not whether the patient receives active tDCS or sham. The study statistician and the DSMB will have a sealed envelope with the intervention group identifiers. This envelope would only be opened if the study statistician is directed to open it by the DSMB or at the end of the futility study.

The randomization will take place centrally via the trial Website (WebDCU). Subjects will be randomized 1:1 (A-tDCS: S-tDCS). The objective of subject randomization is to protect the randomness of treatment allocation and to prevent serious imbalances in site, baseline age, aphasia type, and severity (as measured by the WAB-R). The block urn method (Zhao et al. 2011) and the minimal sufficient balancing method (Zhao et al. 2012) will be used. The computer program developed at the DCU makes the treatment assignment based on the current status of treatment group distribution within each stratum as well as overall balance of treatment assignment. The randomization scheme will never be deterministic.

A “Real-Time” randomization procedure is implemented via the Trial Website on the WebDCU™ System where the clinical center staff enters the basic baseline (e.g., age, aphasia type, and AQ severity) and eligibility information of a subject prior to enrollment. If the subject’s eligibility status is confirmed, the computer program on the WebDCU™ server will evaluate the treatment arm distribution and generate a treatment assignment based on the randomization scheme. The clinician (speech-language pathologist – SLP) enrolling the patient will not see the treatment assignment, only a numeric patient number.

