9. SECONDARY ANALYSES

9.1 Secondary Efficacy Outcome measures

In addition to the primary outcome, several secondary analyses will be conducted. We will examine changes in types of naming errors (defined by the PNT) by tDCS treatment group. The Cinderella story will be analyzed by comparing lexical diversity (VOCD) for nouns, verbs and adjectives; number and types of errors; length and patterns of pauses by treatment group. Pre and post comparisons with both non-aphasic and aphasic speakers from the AphasiaBank database who share a number of demographic features (e.g., type and severity of aphasia, age, etc) will also be made.

At the end of the study, for the interval scale variables, mean change from baseline to immediate post-testing in secondary outcome measures will be reported by treatment group along with the 95%

confidence intervals. Treatment comparisons will be made with a paired *t*-test. For binary variables, the proportion of subjects immediately post-testing will be reported by treatment group along with the 95% confidence intervals.

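### A paired t-test is specified for comparing the two independent arms on the interval-scale secondary outcomes, although no pairs exist

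*Protocol*

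**What the plan says.** Protocol 3.5.1 covers the interval-scale secondary outcomes. Mean change from baseline to "immediate post-testing in secondary outcome measures will be reported by treatment group along with the 95% confidence intervals". The next sentence gives the test: "Treatment comparisons will be made with a paired t-test". SAP 9.1 repeats it: "Treatment comparisons will be made with a paired" t-test.

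The design is parallel-group. In Protocol 2.1, "eligible patients will be randomized to receive either A-tDCS (1 mA) or S-tDCS (placebo) for 15 consecutive weekdays". Protocol 3.2 describes the allocation: "Subjects will be randomized 1:1 (A-tDCS: S-tDCS), controlling for clinical center, aphasia type, and severity". SAP section 6 names the algorithms: "The block urn method (Zhao et al. 2011) and the minimal sufficient balancing method (Zhao et al. 2012) will be used". These methods balance the arms on site, aphasia type and severity (and age, in the SAP). They do not link a patient in one arm to a patient in the other.

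For baseline comparisons of continuous variables, Protocol 3.3 and SAP section 7 name a two-sample t-test or a Wilcoxon rank sum test. The sample size calculation for the primary outcome (Protocol 3.4.3, SAP 8.3) also rests on a two-sample t-test.

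**The concern.** A paired t-test needs a defined partner for each observation. Between these arms there is none, so the sentence can be carried out in only two ways, and neither gives a sound treatment comparison.

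- **Across arms.** The analyst must invent a pairing. This is impossible if the analysed arms differ in size. If they are equal, the p-value depends on the order of the records.
- **Within each arm, before versus after.** The test is then valid for change over time. But both arms receive the same computerised anomia treatment, and sham groups improved in the preliminary studies, so a significant change says nothing about tDCS.

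Nothing else in the plan fills the gap. The longitudinal model in Protocol 3.5.2 and SAP 9.3 is fitted by treatment group, lists no treatment term, and is only optional for the other secondary outcomes. The AphasiaBank comparison concerns external speakers and sets up no one-to-one matching.

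At stake is whether the trial has any pre-specified, reproducible between-arm result for error types, lexical diversity, errors and pauses in connected speech.

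**Working it through.** **Inputs.** From Protocol 3.4.3 and SAP 8.3: SD of change 2.6, sham gains of about 1.2 and 3.9 (4 used for planning), 33 per group inflated to 37, drop-out at most 5%. From Protocol 3.4.2 and SAP 8.2: margin 1.5. All of these concern naming accuracy. The documents give no SD, effect or significance level for the secondary outcomes, so using these inputs with a two-sided 0.05 level is an assumption, for illustration only.

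**1. The plan's own figure.** Two independent samples, one-sided 0.10, difference 1.5, SD 2.6, 33 per group (64 df): power 85.2% by the noncentral t, as stated. The inflation follows from 33/0.95² = 36.6, rounded up to 37. The plan's own calculation thus treats the arms as independent.

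**2. Across arms, average behaviour with 37 arbitrary pairs.** With uncorrelated pairs the standard error is the same for both tests: 2.6 × √(2/37) = 0.604. Only the degrees of freedom change.

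| Test | df | Critical t | 95% CI half-width | Power at 1.5 |
|---|---|---|---|---|
| Two-sample | 72 | 1.993 | 1.205 | 68.7% |
| Paired, arbitrary pairs | 36 | 2.028 | 1.226 | 67.5% |

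The loss is about 1 percentage point. In simulation (4,000 data sets) the false-positive rate was 0.055 for one arbitrary pairing and 0.0545 for the two-sample test.

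**3. Across arms, dependence on record order.** The mean difference does not change with the pairing, but the variance of the paired differences is s₁² + s₂² − 2 × covariance, and the covariance is whatever the chosen order happens to give. With 400 random pairings of each of the 4,000 data sets, order is said to decide the result when more than 2.5% but fewer than 97.5% of pairings are significant:

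| True difference | 0 | 1.0 | 1.5 | 2.0 | 2.5 |
|---|---|---|---|---|---|
| Order decides | 8% | 23% | 21% | 12% | 3% |

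That threshold is a broad one. A single arbitrary pairing disagreed with the two-sample decision less often: about 1%, 4%, 5% and 2.5% of data sets at differences of 0, 1.0, 1.5 and 2.0 (separate run, 1,500 data sets).

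A deliberately borderline example shows the mechanism. With sample means 1.2 apart and both sample SDs exactly 2.6, the two-sample p is 0.051. Over 20,000 pairings the paired p ran from 0.021 to 0.093 (central 95%) and was below 0.05 in 40% of them.

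**4. Unequal arms.** If only observed data were analysed, with independent 5% loss from 37 per arm, the probability of unequal numbers is 1 − Σ P(k)², where P is Binomial(37, 0.95). This gives 0.78. Under the multiple imputation of Protocol 3.4.5 and SAP 8.5, the problem arises only if the randomised numbers differ. That is possible, because the allocation keeps a random element.

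**5. Within arms, same gain in both arms and no tDCS effect.** Noncentrality is gain/(2.6/√37), with 36 df.

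- Gain 1.2: noncentrality 1.2/0.4274 = 2.81. Each arm is significant with probability p = 0.780, both with p² = 0.608, exactly one with 2p(1 − p) = 0.343.
- Gain 4: noncentrality 9.36. Both arms are significant in almost every trial, exactly one in almost none.

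**The case against.** The strongest reply is that this is a one-word slip with little consequence. Software will demand pairs, none exist, and a competent analyst would run the two-sample test already named for baseline comparisons. The SAP is to be updated before database lock and unblinding. The outcomes are exploratory (Protocol 3.4.4, SAP 8.4), and arm means with confidence intervals are reported in any case. This limits the severity. It does not make the stated rule right, because the substitution would be an unplanned departure from a document meant to define the pre-specified analyses.

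The size of the effect is also open to challenge. The inputs belong to naming accuracy, the order-decides threshold is a chosen one, the worked example sits at the significance boundary, and the 0.78 describes an analysis without the planned imputation. All of this stands. The figures show how the test behaves and do not predict results for these outcomes.

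The paragraph can also be read as describing change within each arm, where a paired test is correct and the fault lies only in calling it a treatment comparison. That reading is possible but less natural. It would leave the plan with no between-arm test for these outcomes at all.

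Finally, the plan's practice elsewhere is not uniform. Only the baseline section names a two-sample test as an analysis; the primary analysis is covariate-adjusted, and the pain ratings use a proportional odds model. That is correct, but all of these treat the arms as independent groups.

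**Conclusion.** The concern holds. As written, both documents prescribe a test that cannot be applied between independent arms without inventing pairs, and that does not compare treatments if it is applied within arms. The defect is an undefined, non-reproducible comparison, not lost power: under arbitrary pairing of equal arms, error rates are near nominal and the power loss is about 1 point.

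The effect is confined to the exploratory interval-scale secondary outcomes. The primary analysis, the sample size and the futility decision are untouched. It should be fixed before unblinding, but it does not threaten the trial's main conclusion. The defect itself follows from the design alone and needs no numerical assumption. The illustrative sizes rest on the borrowed SD of 2.6, 37 per arm and a two-sided 0.05 level.

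**What to change.** In Protocol 3.5.1 and SAP 9.1, replace the sentence with wording such as: *Change from baseline in each interval-scale secondary outcome will be compared between arms with a two-sample (unpaired) t-test, and the between-arm difference will be reported with its 95% confidence interval.*

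A model adjusted for the primary analysis covariates would also be valid, and the rank sum test already named for baseline data may suit skewed counts or pause lengths. Whichever is chosen should be named in advance. If a paired t-test is kept, label it as a description of change within each arm and not as a treatment comparison.

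The cost is one sentence in each document, with no extra patients or data. SAP section 2 already provides for an update before database lock and code break.
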